2.2.3 Protocol Deviations

Protocol deviations will be captured by the clinical monitoring team on an ongoing basis throughout the study. All the deviations will be discussed on a case-by-case process, in a Data Review Meeting (DRM) and classified into important and unimportant deviations before the data base lock.

All-important protocol deviations will be listed.

3. PRIMARY AND SECONDARY VARIABLES

3.1 Key Definitions

- The term ‘baseline’ is used to collectively refer to baseline visit or Day 1
 - Baseline visit is the date of informed consent.
 - This will apply to endpoints such as QoL, vital signs, spirometry, oximetry, etc.
 - For patient where there are multiple observations before the baseline visit, last non-missing observation will be used.
 - Day 1 is the date of first dose of Durvalumab. Day 1 can be up to 2 weeks after date of informed consent or may occur on the same date.
 - This will apply to endpoints related to pneumonitis, AEs, or durvalumab.
- Change from baseline will be calculated as follows:
 - Post-baseline value minus baseline value
 - If either the baseline value or post-baseline value is missing, the change from baseline is set to “missing”.
- The last dose date is defined as the last non-missing date where a non-zero dose of durvalumab is given/administered.
- The Study Day is the day relative to the Day 1. Study day will be calculated from date on or after date of Day 1 as follows:
Study day = date of assessment – date of first dose of durvalumab +1 if the date of assessment is on and after the date of first dose of durvalumab; Otherwise, Study day = date of assessment – date of first dose of durvalumab

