5.1 Inclusion Criteria

Patients are eligible to be included in the study only if all of the following inclusion criteria apply:

1. Patient able to provide written signed informed consent prior to any study-specific procedures.
2. Patient must be ≥ 18 years except in the state of Alabama where the legal age is 19 years.
3. Patient has unresectable Stage III NSCLC that has not progressed following concurrent platinum-based chemotherapy and radiation therapy and is eligible to receive durvalumab according to the US FDA approved package insert.
4. Patient will initiate durvalumab treatment within 2 weeks of Baseline and receive at least 1 dose of durvalumab.
5. Patient is able and willing to use the mobile application and connected devices on a daily basis for up to 12 months.
6. Patient is able to complete QoL assessments once every 2 weeks for the first 3 months of the study and monthly thereafter.

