7 STUDY CONDUCT

7.1.1 Enrollment

Patients who are potentially eligible for enrollment will be contacted by qualified site personnel to gauge their interest in joining the study. Interested patients will be screened during their routine care visit, at which time they will be able to ask questions.

After explanation of the study by qualified site personnel, patients wishing to join the study will be asked to sign a study-specific ICF. Baseline information about the patient, including demographic data, relevant treatment and medical history, height, weight, vital signs (temperature, heart rate, respiratory rate, and blood pressure), oxygen saturation (pulse oximetry), pulmonary function (spirometry), and QoL measurements at time of visit, will be collected.

All patients enrolled will continue to receive routine standard of care treatment for NSCLC as per their treating physician's discretion. All patients will receive appropriate training on the devices and tablet application used in the Current Wearable Health Monitoring System. Patients will receive technology for home use and will otherwise continue to receive routine standard of care treatment for NSCLC as per their treating physician's discretion. Each site will be provided with appropriate training materials and support.

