7.4 Study Procedures

7.4.1 Medical Devices

The medical device provided for use in this study is the Current Wearable Health Monitoring System.

- Manufacturer: Current Health Ltd.

The product codes associated with FDA authorization of the device are shown in Table 2.

Table 2 Product Codes associated with the Current Wearable Health Monitoring System

BZG	Spirometer, Diagnostic
BZQ	Monitor, Breathing Frequency
DQA	Oximeter
DRG	Transmitters And Receivers, Physiological Signal, Radiofrequency
MSX	System, Network And Communication, Physiological Monitors
FLL	Thermometer, Electronic, Clinical

Patients enrolled in the study will use the following electronic devices:

- Spirometer (Spirobank G as part of the Current Wearable Health Monitoring System)
- Multiparametric wearable device (as part of the Current Wearable Health Monitoring system)
- Tablet (application installed on tablet is part of the Current Wearable Health Monitoring system)

The Current Wearable Health Monitoring System is intended for:

- Continuous monitoring of the following parameters in adults:
 - Pulse rate (*Multiparametric wearable device*)
 - Oxygen saturation (*Multiparametric wearable device*)
 - Skin temperature (*Multiparametric wearable device*)
 - Movement (*Multiparametric wearable device*)
- Intermittent monitoring in adults of:
 - Respiration rate (*Multiparametric wearable device*)
 - Lung function & spirometry (*Spirobank G Spirometer*)
 - Non-invasive blood pressure (*feature not used in this study*)
 - Weight (*feature not used in this study*)

Training for the patients on the above devices and application will be provided by the investigative site personnel. Qualified site personnel as identified by the PI will review data collected by the devices once daily during business hours (exempting office closures, such as holidays, weekends, etc.), and will contact patients if a clinical intervention is necessary or if there are other issues related to study procedures. However, patients will be advised to contact their treating physicians directly if they are experiencing new or worsening of existing AE-related-symptoms. Technical support will be provided by the study site and Current Health Call Center as described in [Section 7.1.3](#).

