8.2.1 Patient Informed Consent

The physician at each site will ensure that the patient is given full and adequate oral and written information about the nature, purpose, possible risk, and benefit of the study via the Informed Consent Process. Patients must also be notified that their participation is voluntary and they are free to discontinue from the study at any time. The patients should be given the opportunity to ask questions and allowed time to consider the information provided. The patients will be required to sign a statement of informed consent that meets the requirements of US FDA Code of Federal Regulations (CFR) 21CFR 50, local regulations, Health

Insurance Portability and Accountability Act (HIPAA) requirements, where applicable, and the IRB or study site.

Patients will be asked to contact the study site for issues related to study procedures or technical support. The study site will facilitate connection with the Current Health Call Center for assistance, as necessary. For medical questions or to report AE signs/symptoms, patients will be asked to contact their treating physicians directly.

It will be clearly explained to the patient that the study aims to collect data using certain devices, but that the use of these devices will not involve any additional risk for the patient. Patients will also be required to complete QoL and CCI [REDACTED] pertaining to the devices. The frequency of those measurements, the methods to guarantee no personal data are disclosed, and the right of the patient to access his/her information at any time during the study will all be communicated to the patient in a clear and unambiguous way.

The signed and dated patient ICF must be obtained before device onboarding for the study is performed.

The physician or designated site personnel must store the original, signed ICF. A copy of the signed ICF must be given to the patient at the time of consent.

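### The SAP 3.1 baseline rule cannot select an earlier device reading, leaves untreated readings between consent and first dose out of the baseline, and conflicts with the SAP's own windows

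*SAP*

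**What the plan says.** SAP 3.1 lets the word baseline stand for two dates. For clinical measurements it is the baseline visit: "Baseline visit is the date of informed consent", and "This will apply to endpoints such as QoL, vital signs, spirometry, oximetry, etc". Where there are several values, "For patient where there are multiple observations before the baseline visit, last non-missing observation will be used". The other date, Day 1, is the first durvalumab dose, and "Day 1 can be up to 2 weeks after date of informed consent or may occur on the same date". Protocol 5.1 has the same gap: "Patient will initiate durvalumab treatment within 2 weeks of Baseline and receive at least 1 dose of durvalumab".

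On when device data can begin, Protocol 8.2.1 states: "The signed and dated patient ICF must be obtained before device onboarding for the study is performed". Protocol 7.1.1 lists what is collected at enrolment: "vital signs (temperature, heart rate, respiratory rate, and blood pressure), oxygen saturation (pulse oximetry), pulmonary function (spirometry), and QoL measurements at time of visit". It does not say which of these values come from the study devices.

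Three other parts of the SAP bear on the same definition:

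- 4.2.2.9 (QoL) gives baseline an analysis window with no lower limit, ending below study day 1.
- 4.2.4.7 averages daily spirometry and oximetry compliance over the windows of 4.2.2.9, but schedules those daily readings only from Day 1.
- 4.2.4.2 reports baseline oxygen saturation as a median from the device, without saying over what period.

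Protocol Table 1 labels the baseline visit itself Day 1.

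**The concern.** Protocol 2.1 says the devices are meant to track change in each patient's own vital signs and respiratory function, so the reference value matters. A rule that looks for values before the consent date cannot find any from a device issued after consent. What remains is a value from the consent day, and the SAP does not say whether that is a device or a clinic value. Later readings taken before the first dose, the only other untreated device data, are left out of the baseline.

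Two things would be at stake. First, if the baseline is a single reading, its full measurement error enters every later change for that patient. Second, two programmers following different sections could derive different baselines for the same patient, both for change from baseline and for the patient-level compliance rate in SAP 4.2.4.7, which needs an evaluable baseline.

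**Working it through.** **1. What the rule can select.** By SAP 3.1 the baseline visit is the consent date. By Protocol 8.2.1 the earliest device reading is on that date, after signature. The set of device readings from any earlier day is therefore empty. The candidates left are a consent-day device reading or a clinic value from the same visit.

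**2. Length of the untreated period.** SAP 3.1 computes study day as assessment date minus first-dose date, adding 1 only on or after the dose date. With the longest gap, consent falls on study day 0 − 14 = −14. Pre-dose days run from −14 to −1, which is 14 days, or 13 after the consent day. With dosing on the consent date there are none.

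**3. The sections side by side.**

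| Patient | SAP 3.1 baseline | SAP 4.2.2.9 window (below study day 1) |
|---|---|---|
| Dosed 14 days after consent | consent day only (study day −14) | all of study days −14 to −1 |
| Dosed on the consent day | that day (study day 1) | no baseline value; study day 1 falls in the Week 2 window (1 to 21) |

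The two rules disagree in both cases. The oxygen saturation median in 4.2.4.2 fits either rule only if its period is stated, and it is not.

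**4. Size of the effect on change from baseline.** The plan gives no figure to reproduce and no within-patient variability, so the inputs here are assumptions. Let s be the day-to-day SD within a patient, let the baseline be the mean of k pre-dose daily readings with first-order autoregressive correlation ρ, and take the later reading as independent of them. Then

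SD(change) = s × √(1 + v), where v = (1/k²) × Σᵢ Σⱼ ρ^|i−j|, summed over the k days.

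For k = 1, v = 1 and the SD is √2 × s = 1.414s. For ρ = 0, v = 1/k: at k = 7, √(1 + 1/7) = 1.069, and 1 − 1.069/1.414 = 24%.

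| ρ | k = 3 | k = 7 | k = 14 |
|---|---|---|---|
| 0 | 1.155s (18% lower) | 1.069s (24%) | 1.035s (27%) |
| 0.3 | 1.219s (14%) | 1.114s (21%) | 1.061s (25%) |
| 0.6 | 1.296s (8%) | 1.193s (16%) | 1.117s (21%) |
| 0.8 | 1.353s (4%) | 1.281s (9%) | 1.203s (15%) |

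These are for a mean. For a median with independent normal errors, simulation gives reductions of about 22% at k = 7 and 26% at k = 14. With k = 1, as for a patient dosed on the consent day, the reduction is zero.

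**The case against.** The strongest reply is that SAP 3.1 is loosely worded rather than wrong in effect. Several parts of this stand.

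- **Other sections are more generous.** The 4.2.2.9 window takes in all pre-dose days, and 4.2.4.7 borrows it for the devices. So the baseline is not cleanly fixed at consent throughout the SAP. This stands, and it makes the point an inconsistency as well as an unworkable rule.
- **A single reading is not the general case.** SAP 4.2.4.2 already uses a device median for oxygen saturation, and Protocol 7.4.1 lists pulse rate, oxygen saturation and skin temperature as continuously monitored. The single-reading argument applies mainly to spirometry.
- **The untreated readings may be few.** Two weeks is a maximum, the documents give no distribution of the gap, and 4.2.4.7 expects daily readings only from Day 1.
- **No unredacted analysis computes device change from baseline.** The device summary (SAP 4.2.3.4) is redacted, and SAP 6 places the regression models outside this SAP. Another rule may exist there.

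A reader might infer that up to two weeks of device data are discarded. The documents support only that such data are not used as baseline under 3.1; use elsewhere cannot be excluded. A reader might also infer that clinic values are subtracted from device values, for instance clinic temperature against the wearable's "Skin temperature". Nothing prevents this, but no section says it is done. Nor can it be said that a patient whose first valid reading comes the day after consent has no evaluable baseline for compliance: under the 4.2.2.9 window that reading counts if it is pre-dose, and part of 4.2.4.7 is redacted.

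None of this gives the 3.1 rule an earlier device reading to select or reconciles it with 4.2.2.9.

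**Conclusion.** The point holds in this limited form. For device-measured variables the SAP 3.1 rule can select no reading from before the consent day, it leaves untreated readings between consent and first dose out of the baseline, and it conflicts with the window in 4.2.2.9 and sits unclearly beside the device median in 4.2.4.2.

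The likely gain from a multi-day baseline is a 9% to 27% lower SD of change for means of 7 to 14 readings. This rests on assumed correlations of 0 to 0.8, complete daily readings over those days and a single-reading comparator. The upper end is a best case.

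The reach is narrow: device change-from-baseline summaries, possibly the exploratory models, and possibly the compliance baseline. The primary endpoint, pneumonitis by grade counted from Day 1, does not use a device baseline and is unaffected, as are the sample size and the intervals in Protocol Table 4. The correction should be made because it is cheap and removes an ambiguity in the reference value for the device data.

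**What to change.** In SAP 3.1, for variables measured by the study devices:

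- Define baseline as the median of all valid readings from the same device from onboarding to before the first durvalumab dose.
- Use the consent-day device reading as fallback where it is the only one, including when dosing is on the consent day.
- State that clinic values are not used as baseline for device values.
- Report the number of baseline readings per patient.

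Then align the baseline window in 4.2.2.9 (including the same-day-dosing case), state the period of the oxygen saturation median in 4.2.4.2, and state in 4.2.4.7 which readings count as baseline for compliance.

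The cost is SAP wording and programming, with no new data collection. The drawback is that the number of baseline readings, and so the precision of the baseline, will vary between patients, from 1 to about 14 with one reading a day.

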3.2 Missing Data

For AEs and concomitant medications with missing start and/or end dates, the following rules will be applied:

For medication and AE, imputation of end date is not necessary if it is ongoing. If the ongoing flag is missing, then assume that AE is still present/medication is still being administered (i.e., do not impute a date).

Check the data captured in the following fields in the CRF:

- “Was this medication taken as a result of an adverse event”
If the response is “yes”, concomitant medication partial/missing start/end dates can be imputed by referring to related AE number, and vice versa.
- “Was this taken for a condition reported as medical history”
If the response is “yes”, concomitant medication partial/missing start/end dates can be imputed by referring to related medical history number.

If the responses to the above questions are “no” or do not allow imputed values, the following rules will be applied:

Partial/missing start date:

- Missing day - impute the first day of the month unless month is same as month of Day 1 then impute date of Day 1.
- Missing day and month – impute 1st January unless year is the same as Day 1 then impute date of Day 1.
- Completely missing – impute date of Day 1 unless the end date suggests it could have started prior to Day 1 in which case impute the 1st of January of the same year as the end date.
- When imputing a start date ensure that the new imputed date is sensible i.e., it is prior to the corresponding end date if known.

Partial/missing end date:

- Missing day - impute the last day of the month unless month is same as month of study exit then impute date of study exit.
- Missing day and month – impute 31st December unless year is the same as date of study exit then impute date of study exit.
- Completely Missing – For the concomitant medication, if start date is prior to Day 1 then impute date of Day 1, if it started on or after Day 1 then follow the above rule for missing day and month. For the adverse event, the end date will not be imputed.
- Note - for AE, duration would not be calculated.

These imputed dates will be used to determine whether the AEs are treatment emergent or if medications are concomitant. Missing safety data will be treated as missing. However, safety assessment values of the form of “< x” (i.e., below the lower limit of quantification) or > x

(i.e., above the upper limit of quantification) will be imputed as “x” in the calculation of summary statistics but displayed as “< x” or “> x” in the listings.

3.3 Study Endpoints

The definition and analysis of endpoints listed below are described in detail in section 4.2.

The endpoint used to address the primary objective is:

[figure not shown]
- Occurrence of pneumonitis (either radiation or immune-mediated, by grade).
 - Grade of pneumonitis at diagnosis and highest grade of pneumonitis

The endpoints used to address the secondary objectives are:

- Occurrence of pulmonary AEs, including diagnoses of events, by grade
- Duration (days) of pulmonary AEs by type and grade
- Permanent discontinuation of durvalumab due to pulmonary AEs, including pneumonitis
- Early discontinuation of durvalumab treatment for any reason
- Duration (days) of durvalumab treatment
- Treatment interruptions, duration (days) of interruptions, and the reason for interruptions that will be captured in a standard data management form with the site physician documenting reasons in patient charts
- Time (days) to development of Grade 3 to 5 AEs, including pneumonitis
- Prescription of medication used to manage pulmonary AEs and duration (days) of treatment
- Change in QoL scores from baseline

The endpoints used to address the exploratory objectives are:

CCI

4. ANALYSIS METHODS

4.1 General principles

All analyses of the primary, secondary, and exploratory endpoints will be descriptive only with no formal statistical testing. Where appropriate, continuous variables will be summarized using the number of observations (n), mean, standard deviation (SD), median, minimum, and maximum. Categorical variables will be summarized using number of observations (n), frequency and percentages of patients for each category. The 95% CI will be calculated for means, percentages, rates, event-time endpoints by t-distribution/z-distribution, Clopper-Pearson exact method, chi-square distribution, and Kaplan-Meier method respectively where appropriate.

Table 1 Summary of outcome variables and analysis methods

Outcome variable	Analysis Method
Frequency of pneumonitis / pulmonary AEs by grade	Clopper-Pearson exact method
Duration (days) of pneumonitis / pulmonary AEs by type and grade	Kaplan Meier Method
Frequency of interruptions, duration (days) of interruptions, and the reason for treatment interruption	Summary Statistics
Time (days) to onset of Grade 3 to 5 AEs	Kaplan Meier Method
Change in QoL assessment scores from baseline	t-distribution / z-distribution

4.2 Analysis methods

4.2.1 Primary Endpoint and Analysis

The primary endpoint is occurrence of treatment-emergent pneumonitis by grade (grade of pneumonitis at diagnosis and highest grade of pneumonitis).

Definition of pneumonitis event:

- Pneumonitis is defined as a pneumonitis AE recorded in the CRF. An AE episode start from onset date of an AE record and stop at the date when AE is resolved.

List of pneumonitis terms can be found in section 8.2.

- Pneumonitis at diagnosis is defined as the earliest onset of pneumonitis AE on or after Day 1, or onset of subsequent AE episode after previously resolved AE.
- Highest CTCAE grade of pneumonitis is defined as the pneumonitis AE with the highest CTCAE grade from on or after Day 1 per AE episode. Pneumonitis with the highest grade can occur on the same date or after the earliest pneumonitis.
- Patient with response “yes” to CRF question “Is this baseline condition suggestive of pneumonitis?” and the condition is on-going will not be included in this analysis.

Where there are only limited number of pneumonitis, listing will be provided including relevant dates, CTCAE grade, and duration (section 4.2.2.2), etc.

Where there are sufficient number of pneumonitis, frequency and percentage (95%CI) of patients with pneumonitis will be summarized by CTCAE grade for pneumonitis at diagnosis, and highest CTCAE grade of pneumonitis.

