8.3.1.1 Definition of Adverse Event and Serious Adverse Event for Drugs

An AE is the occurrence of an undesirable medical condition or the deterioration of a pre-existing medical condition following or during exposure to a pharmaceutical product or device, whether or not considered causally related to the product or device. An undesirable medical condition can be symptoms (e.g., nausea, chest pain), signs (e.g., tachycardia, enlarged liver), or the abnormal results of an investigation (e.g., laboratory findings,

electrocardiogram). In clinical studies, an AE can include an undesirable medical condition occurring at any time after the Baseline visit (Day 1) once the patient signs the ICF, even if no study treatment has been administered. A treatment-emergent AE (TEAE) is an AE that starts or worsens at any time after initiation of a pharmaceutical product on the first day of treatment through the End-of-Study visit.

An SAE is an AE occurring during any study phase after the patient signs the ICF (i.e., at Baseline, treatment, washout, follow-up) that fulfills 1 or more of the following criteria:

- Results in death
- Is immediately life-threatening
- Requires in-patient hospitalization or prolongation of existing hospitalization
- Results in persistent or significant disability/incapacity or substantial disruption of the ability to conduct normal life functions
- Is a congenital abnormality or birth defect
- Is an important medical event that may jeopardize the patient or may require medical intervention to prevent 1 of the outcomes listed above

Adverse Events (AEs) for malignant tumors reported during a study should generally be assessed as SAEs. If no other seriousness criteria apply, the “Important Medical Event” criterion should be used. In certain situations, however, medical judgement on an individual event basis should be applied to clarify that the malignant tumor event should be assessed and reported as a non-serious AE. For example, if the tumor is included as medical history and progression occurs during the study, the AE may not fulfil the attributes for being assessed as serious, although reporting of the progression of the malignant tumor as an AE is valid and should occur.

Life-threatening in this context refers to a reaction in which the patient was at risk of death at the time of the reaction; it does not refer to a reaction that hypothetically might have caused death if more severe.

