9.2 Populations for Analyses

Planned analysis population sets are described in Table 5 .

Table 5 Analysis Populations

Population	Description
Full Analysis Set (FAS)	All enrolled patients who take at least 1 dose of durvalumab and who have any post-baseline assessment (safety or otherwise).
Safety Analysis Set (SAF)	All enrolled patients who take at least 1 dose of durvalumab

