2. ANALYSIS SETS

2.1 Definition of Analysis Sets

2.1.1 Safety Analysis Set

The Safety Analysis Set (SAF) will include all enrolled patients who take at least 1 dose of durvalumab.

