4.2.2 Secondary Endpoints and Analyses

4.2.2.1 Occurrence of pulmonary AEs, including diagnoses of events, by grade

Definition of pulmonary AE:

- Pulmonary AE is defined as pulmonary adverse event recorded in the CRF. For this study, pulmonary AE do not include pneumonitis event. An AE episode start from onset date of an AE record and stop at the date when AE is resolved. List of terms for pulmonary event can be found in section 8.3.
- Pulmonary AE at diagnosis is defined as the earliest onset of pulmonary AE on or after Day 1, or onset of subsequent AE episode after previously resolved pulmonary AE.
- Highest CTCAE grade of pulmonary AE is defined as the pulmonary AE with the highest CTCAE grade from on or after Day 1 per AE episode. Pulmonary AE with the highest grade can occur on the same date or after the earliest pulmonary AE.
- Patient with response “yes” to CRF question “Is this baseline condition suggestive of a respiratory disease?” and the condition is on-going will not be included in this analysis.

Where there are only limited number of pulmonary AE, listing will be provided including relevant dates, CTCAE grade, and duration, etc.

Where there are sufficient number of pulmonary AE, frequency and percentage (95%CI) of patients with pulmonary AE will be summarized by CTCAE grade for pulmonary AE at diagnosis, and highest CTCAE grade of pulmonary AE and by relationship with pneumonitis.

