4.2.4.8 Adverse Events

An AE for drugs is the occurrence of an undesirable medical condition or the deterioration of a pre-existing medical condition following or during exposure to a pharmaceutical product or device, whether or not considered causally related to the product or device. An AE for medical devices is any untoward medical occurrence, unintended disease or injury, or any untoward clinical signs (including an abnormal laboratory finding) in patients, users, or other persons whether or not considered related to the medical device. This includes events considered related to the medical device and events considered related to the study procedures involved. AEs will be collected throughout the study, from informed consent until 30 days after the End-of-Study visit.

Treatment-emergent adverse events (TEAEs) are defined as any AEs that occur or worsen at any time after the start of administration of the first dose of durvalumab and through 30 days after the last dose of durvalumab. Treatment-emergent AEs will be characterized based on the onset date relative to each patient's first dose date. For adverse events with incomplete start dates, the imputed dates will be used to determine whether the adverse events are treatment emergent.

Adverse events will be summarized by the SOC and PT based on the MedDRA dictionary version 22.1 or later. The CTCAE grades will be summarized by SOC and PT, using the current version of National Cancer Institute (NCI) CTCAE. For summaries by SOC and PT, a patient will be counted once at the SOC level and once at each PT within the SOC level. For

summaries by SOC, PT, and CTCAE Grade, a patient will be counted once at the highest grade for which the event occurred at the SOC level and the highest grade for each unique PT within that SOC level. Therefore, patients may only contribute once to each PT and once to each SOC level. The summaries presenting frequency of AEs by SOC and PT will be ordered by overall descending frequency of SOC and then, within a SOC, by overall descending frequency of PT.

The following AE tables will be provided:

- TEAEs, overall and by SOC and PT
- TEAEs related to pneumonitis by maximum relationship, overall and by SOC and PT
- TEAEs related to medical devices by maximum relationship, overall SOC and PT

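### SAP 4.2.1 and 4.2.2.1 leave out patients with an ongoing suspect baseline condition: the first gives a new-onset pneumonitis rate under another name, the second does not give pulmonary AE incidence in the study population, and neither states a denominator

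*SAP*

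**What the plan says.** **Endpoint.** SAP 4.2.1: "The primary endpoint is occurrence of treatment-emergent pneumonitis by grade". Events are dated by onset: "Pneumonitis at diagnosis is defined as the earliest onset of pneumonitis AE on or after Day 1", or the onset of a further episode once an earlier one has resolved. Worsening is not mentioned.

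**Definition of treatment-emergent.** Protocol 8.3.1.1: "A treatment-emergent AE (TEAE) is an AE that starts or worsens at any time after initiation of a pharmaceutical product". SAP 4.2.4.8: "any AEs that occur or worsen at any time after the start of administration of the first dose of durvalumab". The SAP section then adds that such events are classified by onset date relative to the first dose.

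**Pneumonitis exclusion.** Under its definition of a pneumonitis event, SAP 4.2.1 takes patients whose CRF shows a baseline condition suggestive of pneumonitis and ends "and the condition is on-going will not be included in this analysis".

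**Pulmonary AE exclusion.** SAP 4.2.2.1 ends the same way, but the trigger is the CRF question "Is this baseline condition suggestive of a respiratory disease". The events analysed are the 37 terms in SAP 8.3. The matching secondary objective (SAP 1.1.2) is the incidence of pulmonary AEs by grade; the term treatment-emergent is not used there.

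**Populations.** SAP 2.1.1: "The Safety Analysis Set (SAF) will include all enrolled patients who take at least 1 dose of durvalumab". It is the only analysis set in the SAP; Section 6 drops the protocol's full analysis set. Neither set excludes anyone for a baseline condition. SAP 4.2.1 and 4.2.2.1 promise percentages with confidence intervals but give no denominator. The readable part of SAP Section 6, which is partly redacted, does not list the exclusions as a change.

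**The concern.** A patient who enters with a low-grade condition suggestive of pneumonitis, and in whom it worsens on durvalumab, meets both documents' wording for treatment-emergent. That patient is nevertheless absent from the primary table. What remains is a rate of new-onset pneumonitis among patients with no such condition. That is a reasonable quantity, but not the one named.

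The pulmonary AE rule is the stronger problem. It is triggered by any ongoing condition suggestive of respiratory disease, yet it removes the patient for every event on the SAP 8.3 list. Someone with mild asthma at baseline who develops, say, organising pneumonia on treatment would not appear, although the event is new and of another type. Calling the table new-onset would not cure this.

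The missing denominator adds a second ambiguity. The sentence most naturally means that the patient leaves the analysis, giving the Safety Analysis Set minus those patients. But it is listed under an event definition, so it could also mean that the patient stays in the denominator and is not counted as a case. Two programmers could follow the text and report different percentages. Protocol 4.2 looks to the primary endpoint when deciding on a larger trial, so the quantity described should be unambiguous.

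**Working it through.** **1. The plan's own figure.** Protocol Table 4 gives two-sided exact 95% intervals for n = 75. For 0/75 the upper limit is 1 - 0.025^(1/75) = 4.8%, as stated. All 12 rows reproduce to 0.1 point. The table therefore assumes that all 75 patients are in the denominator.

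**2. Who can be affected.** SAP 2.2.2 bars interstitial lung disease, which is itself one of the six pneumonitis terms in SAP 8.2. It also bars systemic immunosuppressants and conditions that required systemic immunosuppression. This narrows the 4.2.1 exclusion, possibly to nobody. Residual toxicity from chemoradiotherapy is barred only above Grade 2, and COPD and asthma are named only in severe form. The 4.2.2.1 exclusion can therefore apply to enrolled patients. How many is not in the documents.

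**3. Size, any grade.** Let p = 33.9%, the any-grade durvalumab rate cited in Protocol 2.2. Let e be the share left out and RR their risk relative to the others; both are assumed.

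- Rate among those kept: p0 = p / ((1 - e) + e × RR). This is reported if the others leave numerator and denominator.
- Rate if they leave the numerator only: p0 × (1 - e).

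Example: e = 8/75, RR = 2 gives 0.339 / (0.8933 + 0.2133) = 30.6%, and 30.6% × 0.8933 = 27.4%.

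| Left out | Denominator | RR 0 | RR 0.5 | RR 1 | RR 1.5 | RR 2 |
|---|---|---|---|---|---|---|
| 8 of 75 | reduced | 37.9% | 35.8% | 33.9% | 32.2% | 30.6% |
| 8 of 75 | kept at 75 | 33.9% | 32.0% | 30.3% | 28.8% | 27.4% |
| 4 of 75 | reduced | 35.8% | 34.8% | 33.9% | 33.0% | 32.2% |
| 4 of 75 | kept at 75 | 33.9% | 33.0% | 32.1% | 31.3% | 30.5% |

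With 8 left out the shift is 37.9 - 33.9 = +4.0 to 30.6 - 33.9 = -3.3 points (reduced), or 0 to 27.4 - 33.9 = -6.5 points (kept).

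**4. Against sampling error.** 25/75 = 33.3% has an exact interval of 22.9% to 45.2%, about 10 to 12 points either side. The shifts above lie inside it. Only an extreme assumption exceeds it: 15 left out and all of them cases gives 10/60 = 16.7%, or 10/75 = 13.3%. Nothing in the documents points to that.

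**5. Sparse rows.** Protocol 2.2 cites 3.4% for Grade 3 or 4; 0.034 × 75 = 2.55, or about 3 patients. 3/75 = 4.0% (0.8% to 11.2%). If one of the three is a worsening among 4 patients left out, the row reads 2/71 = 2.8% (0.3% to 9.8%) or 2/75 = 2.7% (0.3% to 9.3%).

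**6. Zero-event limit.** If patients leave the denominator, the 4.8% limit becomes 1 - 0.025^(1/67) = 5.4% with 8 left out and 1 - 0.025^(1/60) = 6.0% with 15 left out.

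**The case against.** The exclusions are explicit and pre-specified, and leaving out patients who already have a condition is a standard way to estimate new onset. SAP 4.2.4.8 itself classifies treatment-emergent events by onset date, so the tension over worsening already exists inside that section. The plain reading of the denominator is the Safety Analysis Set minus the excluded patients. SAP 4.2.2.2 adopts the pulmonary AE definition of 4.2.2.1, so carry-over to duration is largely settled. The study is a descriptive pilot without testing; with few events there will be a listing and no percentage. All AEs are listed, and treatment-emergent AEs and CTCAE grades are summarised by system organ class and preferred term.

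Much of this stands, and it limits the point. Three stronger readings are tempting but unsupported:

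- A reader might infer that both tables misreport a treatment-emergent rate. That label is attached only to pneumonitis. For pulmonary AEs the mismatch is with the incidence objective.
- A reader might infer that the primary rate is understated. The direction depends on the risk of those left out and on the denominator, and if nobody is left out the rates coincide.
- A reader might infer that these patients' events vanish. They remain in the listings. What the tables by preferred term do not give is the six pneumonitis terms pooled into one by-grade rate with its interval.

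The objection does not explain why a new-onset rate carries another name, or why an ongoing respiratory condition should remove a patient for an unrelated new event.

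**Conclusion.** The point holds and should be fixed. The text is clear on two matters: 4.2.1 yields a new-onset rate under a treatment-emergent label, and 4.2.2.1 yields something narrower than the incidence of pulmonary AEs in the patients studied. Two things are left open: the denominator in both sections, and whether the exclusions apply to the time to Grade 3 to 5 events in SAP 4.2.2.7, which refers back to them without saying so.

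The practical size is unknown. The shifts of a few points rest on an assumed 8 of 75 left out, RR 0 to 2 and a true rate of 33.9%, and are smaller than sampling error. They are a change in what is being estimated, however, which the confidence interval does not show. They arise only if events are numerous enough for a percentage table. The case for change therefore rests on naming the quantity correctly and fixing the denominator, not on a demonstrated material bias.

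**What to change.** - Report both by-grade rates in all Safety Analysis Set patients and state that denominator in 4.2.1 and 4.2.2.1.
- Count as events: (1) any listed term with onset on or after Day 1 that was not ongoing at baseline; (2) a new episode after resolution; (3) a recorded worsening above the baseline CTCAE grade.
- Keep the subset with no ongoing baseline condition as a sensitivity analysis labelled new-onset, showing how many patients each rule leaves out and the resulting denominator.
- State whether the exclusions apply in 4.2.2.7.
- Leave the onset date for durations in 4.2.2.2 as recorded in the CRF, and flag worsened baseline conditions separately.
- Record the change in SAP Section 6.

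The cost is SAP wording and one extra table. Protocol 8.3.1.3 has baseline severity documented only where possible and does not list a date of grade change among the items collected. Some worsenings will therefore lack a baseline grade or a date and need a stated fallback, such as counting a recorded worsening when the baseline grade is missing, or a listing.
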